#### 3.5 Assessments

Unless otherwise indicated, all assessments will be performed by the Investigator or a qualified designee.

Confidential Page 33 of 70

#### 3.6 Schedule of Assessments

The procedures to be performed throughout the study are outlined in the Schedule of Assessments (Table 3).

Confidential Page 34 of 70

**Table 3: Schedule of Assessments** 

| Study Period  | Screen                      | Treatment Period |    |    |    |    |    |    |    |      |                 |      |     |             |      |
|---|-----------------------------|------------------|----|----|----|----|----|----|----|------|-----------------|------|-----|-------------|------|
| In-clinic Visit (V) Telehealth Visit (T)                  | V1                          | V2               | Т3 | T4 | T5 | T6 | T7 | T8 | V9 | T10  | T11             | T12  | V13 | V14         | ET c |
| Day   | Up to
28 Days            | 0                | 1  | 2  | 4  | 7  | 14 | 21 | 30 | 37 b | 44 b | 51 b | 80  | 90
(EOT) |      |
| Visit Window (Days)                                       | Before Random. a |                  |    |    |    | ±2 | ±2 | ±2 | +7 | ±2   | ±2              | ±2   | +2  | +7          |      |
| Informed consent  | X                           |                  |    |    |    |    |    |    |    |      |                 |      |     |             |      |
| Eligibility criteria confirmed                            | X                           | X                |    |    |    |    |    |    |    |      |                 |      |     |             |      |
| Demographics and medical history                          | X                           |                  |    |    |    |    |    |    |    |      |                 |      |     |             |      |
| Randomization   |                             | X                |    |    |    |    |    |    |    |      |                 |      |     |             |      |
| Physical examination, including weight and height         | X                           |                  |    |    |    |    |    |    |    |      |                 |      |     | X           | X    |
| Prior/concomitant medications                             | X                           | X                | X  | X  | X  | X  | X  | X  | X  | X    | X               | X    | X   | X           | X    |
| Smoking status and evaluation of pulmonary toxin exposure | X                           |                  |    |    |    |    |    |    |    |      |                 |      |     | X           | X    |
| Adverse events d  | X                           | X                | X  | X  | X  | X  | X  | X  | X  | X    | X               | X    | X   | X           | X    |
| COVID-19 screening e                           | X                           |                  |    |    |    |    |    |    |    |      |                 |      |     |             |      |
| Hypoglycemic events f                                     | X                           | X                | X  | X  | X  | X  | X  | X  | X  | X    | X               | X    | X   | X           | X    |
| HbA1c (central laboratory)                                | X                           |                  |    |    |    |    |    |    |    |      |                 |      |     | X           | X c  |
| Pregnancy test g                               | X                           |                  |    |    |    |    |    |    |    |      |                 |      |     |             |      |
| TSH test h  | X                           |                  |    |    |    |    |    |    |    |      |                 |      |     |             |      |
| Serum creatinine h  | X                           |                  |    |    |    |    |    |    |    |      |                 |      |     |             |      |

Page 35 of 70

| Study Period  | Screen                         |    | Treatment Period |    |    |    |    |    |    |      |                 |      |     |             |      |
|---|--------------------------------|----|------------------|----|----|----|----|----|----|------|-----------------|------|-----|-------------|------|
| In-clinic Visit (V) Telehealth Visit (T)            | V1                             | V2 | Т3               | T4 | Т5 | Т6 | Т7 | Т8 | V9 | T10  | T11             | T12  | V13 | V14         | ET c |
| Day   | Up to 28 Days                  | 0  | 1                | 2  | 4  | 7  | 14 | 21 | 30 | 37 b | 44 b | 51 b | 80  | 90
(EOT) |      |
| Visit Window (Days)                                 | Before
Random. a |    |                  |    |    | ±2 | ±2 | ±2 | +7 | ±2   | ±2              | ±2   | +2  | +7          |      |
| FEV 1 measurement                        | X                              |    |                  |    |    |    |    |    |    |      |                 |      |     | X           | X    |
| Dispensing and placement of blinded CGM sensors     | X                              |    |                  |    |    |    |    |    |    |      |                 |      | X   |             |      |
| Instruction of subject on blinded CGM procedures    | X                              |    |                  |    |    |    |    |    |    |      |                 |      | X   |             |      |
| Review of blinded
CGM readings and
compliance |                                | X  |                  |    |    |    |    |    |    |      |                 |      |     |             |      |
| Removal and download of blinded CGM                 |                                | X  |                  |    |    |    |    |    |    |      |                 |      |     | X           |      |
| Review/download unblinded CGM data i                |                                | X  |                  |    |    |    |    |    | X  |      |                 |      | X   | X           | X    |
| Review/download
pump data i           |                                | X  |                  |    |    |    |    |    | X  |      |                 |      | X   | X           | X    |

Page 36 of 70

| Study Period  | Screen                      |                | Treatment Period |    |    |    |    |    |    |      |                 |      |     |             |      |
|---|-----------------------------|----------------|------------------|----|----|----|----|----|----|------|-----------------|------|-----|-------------|------|
| In-clinic Visit (V) Telehealth Visit (T)  | V1                          | V2             | Т3               | T4 | T5 | Т6 | Т7 | Т8 | V9 | T10  | T11             | T12  | V13 | V14         | ET c |
| Day   | Up to 28 Days               | 0              | 1                | 2  | 4  | 7  | 14 | 21 | 30 | 37 b | 44 b | 51 b | 80  | 90
(EOT) |      |
| Visit Window (Days)   | Before Random. a |                |                  |    |    | ±2 | ±2 | ±2 | +7 | ±2   | ±2              | ±2   | +2  | +7          |      |
| Remind subjects in the Afrezza + AID group to NOT enter carb intake/meal announcements into their insulin pump j |                             |                | X                | X  | X  | X  | X  | X  | X  | X    | X               | X    | X   |             |      |
| Training on use of the study-provided glucose meter   | X                           |                |                  |    |    |    |    |    |    |      |                 |      |     |             |      |
| Dispense glucose meter and supplies   | X                           |                |                  |    |    |    |    |    |    |      |                 |      |     |             |      |
| Provide additional glucose test strips and lancets, as necessary  |                             | X              |                  |    |    |    |    |    | X  |      |                 |      | X   |             |      |
| Collect and review glucose meter data   |                             | X              |                  |    |    |    |    |    | X  |      |                 |      | X   | X           | X    |
| Instruct subject on logging of meal announcements and Afrezza doses, as applicable  |                             | X j |                  |    |    |    |    |    |    |      |                 |      | X   |             |      |
| Collect information on
meal announcements
and Afrezza doses, as
applicable   |                             |                |                  |    |    |    |    |    |    |      |                 |      |     | X           |      |

Page 37 of 70

| Study Period   | Screen                         |    | Treatment Period |    |    |    |    |    |    |      |                 |      |     |             |      |
|--|--------------------------------|----|------------------|----|----|----|----|----|----|------|-----------------|------|-----|-------------|------|
| In-clinic Visit (V) Telehealth Visit (T)   | V1                             | V2 | Т3               | T4 | T5 | Т6 | Т7 | Т8 | V9 | T10  | T11             | T12  | V13 | V14         | ET c |
| Day  | Up to 28 Days                  | 0  | 1                | 2  | 4  | 7  | 14 | 21 | 30 | 37 b | 44 b | 51 b | 80  | 90
(EOT) |      |
| Visit Window (Days)  | Before
Random. a |    |                  |    |    | ±2 | ±2 | ±2 | +7 | ±2   | ±2              | ±2   | +2  | +7          |      |
| First dose of Afrezza
(Afrezza groups) or
dose of RAA (AID
Control group) with
standardized meal   |                                | X  |                  |    |    |    |    |    |    |      |                 |      |     |             |      |
| Titration of all insulins to glycemic effect   |                                |    | X                | X  | X  | X  | X  | X  | X  | X    | X               | X    | X   |             |      |
|  | Afrezza Groups Only            |    |                  |    |    |    |    |    |    |      |                 |      |     |             |      |
| Training for use and storage of Afrezza  |                                | X  |                  |    |    |    |    |    |    |      |                 |      |     |             |      |
| Training, as needed, on CGM use including but not limited to the use of alerts, interpretation of trends, interfering substances, contraindications, etc |                                | X  | X                | X  | X  | X  | X  | X  | X  | X    | X               | X    | X   |             |      |
| Dispense Afrezza
inhalers and
cartridges, as
necessary  |                                | X  |                  |    |    |    |    |    | X  |      |                 |      | X   |             |      |

Page 38 of 70

| Study Period   | Screen                      |    | Treatment Period |    |    |    |    |    |    |      |                 |      |     |             |      |
|--|-----------------------------|----|------------------|----|----|----|----|----|----|------|-----------------|------|-----|-------------|------|
| In-clinic Visit (V) Telehealth Visit (T)   | V1                          | V2 | Т3               | T4 | Т5 | Т6 | Т7 | Т8 | V9 | T10  | T11             | T12  | V13 | V14         | ET c |
| Day  | Up to 28 Days               | 0  | 1                | 2  | 4  | 7  | 14 | 21 | 30 | 37 b | 44 b | 51 b | 80  | 90
(EOT) |      |
| Visit Window (Days)  | Before Random. a |    |                  |    |    | ±2 | ±2 | ±2 | +7 | ±2   | ±2              | ±2   | +2  | +7          |      |
| Disbursement/ placement of unblinded CGM sensors k   |                             | X  |                  |    |    |    |    |    | X  |      |                 |      |     |             |      |
| Training on use of unblinded CGM k  |                             | X  |                  |    |    |    |    |    |    |      |                 |      |     |             |      |
| Assess the need for
Afrezza correction
dosing based on CGM
profile  |                             |    | X                | X  | X  | X  | X  | X  | X  |      |                 |      |     |             |      |
| Dispense insulin
degludec and injection
supplies, as necessary
(Afrezza + Insulin
Degludec group only) |                             | X  |                  |    |    |    |    |    | X  |      |                 |      |     |             |      |
| Record basal insulin
dosages (Afrezza +
Insulin Degludec
group only)                                      |                             | X  |                  |    |    |    |    |    | X  |      |                 |      | X   | X           |      |
| Collect Afrezza unused inhalers and cartridges as well as any unopened bottles of insulin degludec                 |                             |    |                  |    |    |    |    |    |    |      |                 |      |     | X           | X    |

Page 39 of 70

AID=automated insulin delivery, CGM=continuous glucose monitoring, COVID-19=coronavirus 2019, EOT=end of treatment, ET=early termination, FEV1=forced expiratory volume in 1 second, HbA1c=glycated hemoglobin A1c, RAA=rapid-acting insulin analog, Random=randomization, Screen=screening, SMBG=self-monitored blood glucose, TSH=thyroid-stimulating hormone.

- a. The Screening Visit should be scheduled 10 days (+ 4 days) before the subject's expected date of randomization. When subjects return for Visit 2, blinded CGM data will be downloaded and CGM sensor wear evaluated. If CGM sensor wear time is inadequate, per the discretion of the Investigator, the Screening Period can be extended (this becomes an unscheduled visit) and sensor wear can be repeated once. The subject will return to the clinic 10 days (+ 4 days) later and, if sensor wear is adequate and all eligibility criteria met, be randomized to study treatment and proceed with the meal challenge and Visit 2 assessments. Visit 2 should be within 4 days of the end of the final sensor wear data (i.e., the CGM sensor with adequate wear time).
- b. The timing of telephone visits T10, T11, and T12 is relative to Visit 9 (T10 should occur 7 days [±2 days] from Visit 9, T11 is 14 days [±2 days] from Visit 9, and T12 is 31 days [±2 days] from Visit 9).
- c. A sample should be collected for HbA1c at the ET visit if the subject discontinues the study after 4 weeks of participation.
- d. Any adverse event that occurs after the subject enrolls in the study (consent date) will be recorded.
- e. Subjects will be asked to provide a recent negative COVID-19 test (if available), confirm they have no symptoms of COVID-19, or provide evidence of COVID-19 vaccination.
- f. Subjects should use their study provided blood glucose meter to take an SMBG value if their CGM reading is <70 mg/dL or if their CGM reading does not match their symptoms or expectations. Hypoglycemic episodes will be defined as all SMBG measurements <70 mg/dL. See Section 3.9.2.6.
- g. A negative urine pregnancy test is required for enrollment, from all female subjects of child-bearing potential. After enrollment, additional pregnancy tests may be conducted as needed at the discretion of the Investigator.
- h. A documented normal level within 6 months of screening can be used in lieu of testing.
- i. CGM reports and pump reports will be downloaded from V1 to V2 at V2, V2 to V9 and 10 days before V9 to V9 at V9, V9 to 30 days after V9 at V13, and 30 days before V14 to V14 and V13 to V14 at V14 using Carelink for Medtronic CGM and pumps. CGM reports/data and pump reports/data will be downloaded from V1 to V2 at V2, V2 to V9 and 10 days before V9 to V9 at V9, V9 to 30 days after V9 at V13, and 30 days before V14 to V14 and V13 to V14 at V14 using Clarity for Dexcom CGM and t:connect for Tandem pumps. The site will de-identify all reports and data.
- j. Subjects in the Afrezza + AID group will be instructed not to enter carb intake/meal announcements in the pump system. In the event that they accidentally enter carb intake/meal announcement for a certain meal, they should NOT dose Afrezza for that same meal. If they accidentally take Afrezza with a meal announcement, carbs or glucagon should be administered. For subjects in the Afrezza + AID group, the site will confirm at every visit (phone or in person) to make sure they are not entering carb intake/meal announcements in the pump system.
- k. Only applies to subjects in the Afrezza + Insulin Degludec group who use a Medtronic 670G/770G system.

Confidential Page 40 of 70

Table 4: CGM/Pump Reports and Data to be Downloaded

| Reports/Data to be Downloaded                 | V2 | V9 | V13 | V14 |
|---|----|----|-----|-----|
| Blinded G6 PRO Data                           | X  |    |     | X   |
| V1 to V2 CGM/pump report/data                 | X  |    |     |     |
| V2 to V9 CGM/pump report/data                 |    | X  |     |     |
| V9 minus 10 Days to V9 CGM/pump report/data   |    | X  |     |     |
| V9 to V9 plus 30 Days CGM/pump report/data    |    |    | X   |     |
| V14 minus 30 Days to V14 CGM/pump report/data |    |    |     | X   |
| V13 to V14 CGM/pump report                    |    |    |     | X   |
| Study Meter Download                          | X  | X  | X   | X   |

Confidential Page 41 of 70

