#### 1.2 Study Rationale

Approximately 40% to 60% of patients with T1DM use continuous subcutaneous insulin infusion (CSII) devices, commonly referred to as insulin pumps (Umpierrez et al. 2018, Miller et al. 2015). CSII devices are computerized devices programmed to deliver an RAA under the skin continuously throughout the day via a catheter attached to a person's abdomen. When used in tandem with continuous glucose monitoring (CGM) this is a closed-loop system. Hybrid closed-loop systems are characterized by the coexistence of algorithm-driven automated insulin delivery (AID) for basal insulin coverage combined with manual mealtime bolus insulin doses.

The current study aims to evaluate mealtime use of Afrezza in adults ≥18 years of age with T1DM who currently use AID. In this study, Afrezza-treated subjects will use two different methods for basal insulin delivery (subcutaneous [SC] injection of long-acting insulin or an AID system with RAA) compared to a control group (without Afrezza) of patients on an AID system with RAA.

Subjects will administer their initial Afrezza dose based on the subject's current insulin-to-carbohydrate (I:CHO) ratio multiplied by 2 and rounded down to the nearest Afrezza dose size, subject to Investigator discretion, but not exceeding 24 units of Afrezza. Pooled Afrezza trial data suggests that subjects achieve similar glycemic control with a dose ratio of 1.5- to 2-fold the equivalent unit value of a subcutaneous insulin analog in head-to-head comparisons (Kendall et al. 2020, Grant et al. 2019), which is significantly higher than the dose conversion in the label. Additionally, a proof-of-concept study was done with 20 patients demonstrating improved postprandial glucose excursions (PPGE) with the higher dose of Afrezza compared to the current label (Afrezza 2020). This higher initial conversion dose of Afrezza will be used for the first dose under medical supervision in the clinic.

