## 3.7.2 Randomization (V2)

When subjects return for Visit 2, blinded CGM data will be downloaded and CGM sensor wear evaluated. If CGM sensor wear time is inadequate, per the discretion of the Investigator, the Screening Period can be extended and sensor wear can be repeated once (this becomes an unscheduled visit). The subject will return to the clinic 10 days (+4 days) later and, if sensor wear is adequate and all eligibility criteria met, be randomized to study treatment and proceed with the meal challenge and Visit 2 assessments. Visit 2 should be within 4 days of the end of the final sensor wear data (i.e., the CGM sensor with adequate wear time).

The following procedures will be performed at Visit 2:

- Enrollment (if eligibility criteria are met)
- Record concomitant medications
- Record current basal insulin dosages
- Remove blinded Dexcom G6 Pro CGM

Download and de-identify data from Dexcom G6 Pro device (

Confidential Page 42 of 70

• )

mannkind

Download and de-identify of unblinded CGM reports and pump reports for Medtronic CGM and pumps (

Confidential Page 43 of 70

mannkind

Download and de-identify of unblinded CGM reports/data and pump reports/data for Dexcom CGM and t:connect for Tandem pumps (

Confidential Page 44 of 70

- )
- Subjects randomized to study treatment (Afrezza + Insulin Degludec, Afrezza + AID, or AID Control)
- Disbursement/placement of unblinded CGM sensor (only applies to subjects in the Afrezza + Insulin Degludec group who use a Medtronic 670G/770G system)
- Conduct 2-hour, in-clinic meal tolerance test
- Subjects will take their first dose of Afrezza or their dose of RAA with standardized meal challenge as described in Section 3.7.2.1.
- Record AEs
- Record any hypoglycemic episodes (see Section 3.9.2.6)
- Provide additional subject training, as needed, on CGM use, including but not limited to the
  use of alerts, interpretation of trends, interfering substances, and contraindications.

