## 3.7.2.1 Meal Challenge

Subjects will come into the clinic in a fasting state for Visit 2, with exception of treating hypoglycemia. Fasting will be defined as no intake of drink or food, with exception of water, for  $\geq$ 6 hours before the clinic visit. Subjects will also be instructed not to administer manual bolus doses of insulin during the 4 hours immediately preceding the meal challenge. If the subject requires a manual bolus insulin dose to correct hyperglycemia within the 4 hours prior to the scheduled visit, the meal challenge will need to be rescheduled.

The CGM glucose value will be confirmed 15 minutes before the start of the meal. If the subject's CGM value is  $\geq$ 70 mg/dL, the subject can start the meal challenge 15 minutes later. If the subject's CGM value is  $\leq$ 70 mg/dL, the Investigator can provide 15 g of fast-acting carbohydrates and reassess the CGM glucose value after 30 minutes and if the subject's new CGM value is  $\geq$ 70 mg/dL, the subject can start the meal challenge 15 minutes later. The CGM value obtained immediately before the start of the meal (defined as t=0) will serve as the baseline glucose value for that visit.

Subjects in the Afrezza groups will receive training on how to use the Afrezza Inhaler using BluHale technology, as well as how to identify and manage any events of hypo and hyperglycemia.

In addition to CGM, subjects will be instructed to take SMBG measurements 15 minutes before the start of the meal, immediately before the start of the meal (t=0), and at 15, 30, 45, 60, 90, and 120 minutes after the start of the meal challenge.

Confidential Page 45 of 70

mannkind

The meal challenge will consist of 1-2 bottles of Boost nutritional shake (1 bottle is approximately 240 calories, 41 g carbohydrate, 10 g protein, and 4 g fat). The meal is to be fully consumed within 15 minutes. Each Afrezza dose will be administered at the start of the meal challenge. The RAA dose will be administered  $10 \pm 5$  minutes (per label) before the start of the meal challenge, per Investigator discretion.

For Afrezza doses exceeding 12 units, inhalations from multiple cartridges are necessary. To achieve the required total mealtime dose, subjects should use a combination of 4-unit, 8-unit, and 12-unit cartridges.

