### 3.9.1 Efficacy Assessments

### 3.9.1.1 Continuous Glucose Monitoring

Subjects will wear a blinded CGM at baseline for up to 20 days during an up to 28-day screening period and during the last 10 days of the study. Additionally, subjects will measure their glucose throughout the study using an unblinded CGM system (sensors, transmitter). Subjects will be instructed at Visit 2 in the operation of their CGM device.

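### General CGM training after Visit 2 and hypoglycemia training are written for the Afrezza groups only, which conflicts with other sections and adds an avoidable education difference from AID Control

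*Protocol*

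**What the plan says.** Table 3 (Protocol Section 3.6) has a block headed "Afrezza Groups Only". Most of its rows concern the supply, use or dosing of Afrezza and degludec. Two rows carry footnote k and apply only to degludec-group subjects who use a Medtronic system. The same block also holds a general row, "Training, as needed, on CGM use including but not limited to the use of alerts, interpretation of trends", marked at V2, T3-T8, V9, T10-T12 and V13.

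Section 3.7.2.1 reads "Subjects in the Afrezza groups will receive training on how to use the Afrezza Inhaler using BluHale technology" and continues "as well as how to identify and manage any events of hypo and hyperglycemia". AID Control is not named there.

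Other sections set no arm limit:

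- Section 3.7.2, at Visit 2: "Provide additional subject training, as needed, on CGM use". Another item in that list names an arm where a limit is meant.
- Section 3.9.1.1: "Subjects will be instructed at Visit 2 in the operation of their CGM device".
- Section 3.9.2.7 has investigators educate subjects about hyperglycemia and DKA, using CGM and meter.
- Section 3.7.2 gives glucagon-kit training to every subject.

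Section 1.2 describes Afrezza-treated subjects "compared to a control group (without Afrezza) of patients on an AID system with RAA".

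**The concern.** All three arms use an unblinded CGM, and all have insulin titrated at the same contacts from T3 to V13. Coaching on alerts and trends is therefore relevant to control subjects as well. Such coaching, and training in recognising low glucose, could plausibly affect HbA1c, time in range and time below range, which are the quantities the trial summarises.

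If sites follow Table 3, both Afrezza groups are scheduled for repeated coaching that AID Control is not. The study is open-label, and the statistical sections shown in the SAP contain no adjustment for training. In a side-by-side reading of the arms, the education difference could not be separated from Afrezza afterwards. Separately, sites have two instructions for a control subject at Visit 2 and cannot follow both.

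**Working it through.** The documents state no figure for this point, so the check is a count and a comparison of passages.

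**Contacts in the CGM training row (Table 3).** V2 (1) + T3-T8 (6) + V9 (1) + T10-T12 (3) + V13 (1) = 12. After Visit 2: 12 − 1 = 11.

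**Titration row (Table 3, above the Afrezza-only block, so all arms).** T3-T8 (6) + V9 (1) + T10-T12 (3) + V13 (1) = 11. These are the same 11 contacts.

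**Subjects.** The 2:2:1 ratio applied to 25 gives 25 × 2/5 = 10, 10, and 25 × 1/5 = 5. By Table 3, 20 subjects are scheduled for the repeated training and 5 are not.

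**Education by arm:**

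| Content | Afrezza groups | AID Control | Where |
|---|---|---|---|
| Operating the CGM, V2 | yes | yes | 3.9.1.1 |
| As-needed CGM training, V2 | yes | yes by 3.7.2; no by Table 3 | 3.7.2 against Table 3 |
| As-needed CGM training, T3-V13 | 11 contacts | none | Table 3 only |
| Hyperglycemia and DKA | yes | yes by 3.9.2.7; not named in 3.7.2.1 | 3.9.2.7, 3.7.2.1 |
| Recognising and managing hypoglycemia | yes | not stated | 3.7.2.1 |
| Glucagon kit | yes | yes | 3.7.2 |
| Fingerstick when CGM is <70 mg/dL | yes | yes | 1.3.3, 3.9.1.2, Table 3 note f |

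The visit lists for T3-T8, V9, T10-T12 and V13 (Sections 3.7.3 to 3.7.6) do not mention CGM training. The Table 3 row is therefore the only source for the 11 later contacts, and no all-subject text offsets its arm limit.

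Scheduled CGM-training contacts per subject are thus 12 in each Afrezza group. In AID Control they are 0 by Table 3, or 1 if Section 3.7.2 governs at Visit 2. Two gaps have no all-subject counterpart: CGM training after Visit 2, and training in recognising and managing hypoglycemia.

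**The case against.** Much of the case on the other side stands.

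- A reader might infer that AID Control gets no education. The documents do not support that. Controls have CGM instruction and, by Section 3.7.2, CGM training at Visit 2. They also have hyperglycemia/DKA education, glucagon training, and telephone contacts at which questions are answered.
- A reader might infer that control subjects would confirm fewer lows by fingerstick, distorting the SMBG hypoglycemia count. The instruction to test at a CGM value <70 mg/dL, and the study meter, go to every subject. Nothing shows that the Afrezza-only row changes that behaviour.
- The training is given only as needed, and 7 of the 12 contacts fall on days 0 to 21 (V2 and T3-T8). Twelve marks are not twelve sessions.
- Some extra CGM support may belong to the regimen. Afrezza correction dosing is assessed from the CGM profile, some degludec-group subjects change CGM, and that group leaves the pump. This justifies arm-specific rows for those tasks. It does not explain why general coaching on alerts and trends stops at Visit 2 for controls.
- The objectives are change within each group, the analysis is descriptive, and no significance is to be derived. No planned analysis is biased, but an informal comparison with the controls gains no protection from being descriptive.
- Equal training would not make every contrast a pure Afrezza contrast. The degludec group also changes its basal delivery, and titration is at investigator discretion. Equal training removes one avoidable difference.

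**Conclusion.** The point holds as an inconsistency with a limited design consequence. Table 3 and Section 3.7.2.1 restrict by arm what Sections 3.7.2, 3.9.1.1 and 3.9.2.7 wholly or partly give to everyone. As written, AID Control lacks 11 scheduled opportunities for CGM training and has no stated training in recognising and managing hypoglycemia.

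The consequence is confined to descriptive comparisons with the control group, most directly Afrezza + AID against AID Control. The within-group summaries remain what the plan says they are: change under each regimen as delivered.

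A reader might want to put an HbA1c figure on the difference, or conclude that the control is invalid. Neither is supported. The documents give no effect of training and no delivered dose, so the size cannot be computed. A direction favouring Afrezza on HbA1c is plausible but not shown. The conclusion assumes that sites work from Table 3. If they train all subjects in practice, the difference shrinks or disappears, and only the conflicting text remains.

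**What to change.** Reconcile Table 3 and Section 3.7.2.1 with Sections 3.7.2, 3.9.1.1 and 3.9.2.7:

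- Move the general CGM training row out of the Afrezza-only block, so that it applies to all three arms at the same contacts.
- Word the hypo- and hyperglycemia education in Section 3.7.2.1 for all subjects.
- Keep inhaler training and the two footnote-k CGM rows arm-specific.

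This changes no dose or treatment rule. The cost is protocol wording and a few minutes of as-needed training for 5 control subjects. At most that is 11 × 5 = 55 contacts after Visit 2, or 12 × 5 = 60 including Visit 2, all already scheduled. If the sponsor intends the difference, the protocol should say so, and the study report should state it as a limitation of any comparison with AID Control.
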